9.3.1 Inclusion Criteria

Subjects must meet all of the following criteria to be included in this study:

1. MCI due to AD or Mild AD according to the National Institute of Aging – Alzheimer’s Association (NIA-AA) core clinical criteria and must have all of the following at Screening: (revised per Amendment 03)
 - a. MMSE score equal to or greater than 24
 - b. CDR global score of 0.5
 - c. CDR Memory Box score of 0.5 or greater
2. A history of subjective memory decline with gradual onset and slow progression over the last 1 year before Screening; this MUST be corroborated by a study partner
3. Cognitive impairment of at least 1 SD from age-adjusted norms in total recall or delayed recall on the ISLT.

4. Positive biomarker for brain amyloid pathology as indicated by at least 1 of the following:
 - a. PET assessment of amyloid imaging agent uptake into brain. Note: amyloid PET screens will be performed according to local regulatory guidelines and thus may be restricted for those subjects who are not suitable for LP to obtain CSF for testing of eligibility.
 - b. CSF AD assessment (eg, A β (1-42), tau: A β (1-42) ratio) (revised per Amendment 03)
NOTE: Subjects may undergo both the amyloid PET and CSF assessments, but need a positive amyloid result in only 1 of the 2 procedures to confirm eligibility. Subjects who consent to amyloid PET or CSF for eligibility purposes are not required to participate in the amyloid PET or CSF longitudinal substudies. Use of a historical amyloid positive PET (conducted within 12 months before the planned date of randomization) is acceptable for determination of eligibility but will not suffice for the baseline assessment if the subject wishes to consent to the amyloid PET longitudinal substudy. (revised per Amendment 03) The historical imaging data must be made available to the sponsor.
5. Male or female subjects between 50 and 85 years of age, inclusive at the time of consent
6. If receiving an AChEI or memantine or both for AD, must be on a stable dose for at least 12 weeks prior to Randomization. Treatment-naïve subjects with AD can be entered into the study.

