9.4.7 Prior and Concomitant Therapy

Any medication (including over-the-counter medications) or therapy administered to the subject prior to the study (within 6 months of randomization) and during the study (starting at the date of informed consent) will be recorded on the Prior & Concomitant Medication eCRF or Non-Pharmacological Procedures eCRF. The investigator will record on the Adverse Event eCRF any AE for which the concomitant medication/therapy was administered. If the concomitant medication/therapy is being administered for a medical condition present at the time of entry into the study, the investigator will record the medical condition on the Medical History and Current Medical Condition eCRF.

Listings of prohibited and permitted drugs are provided in [Appendix 2](#) (Prohibited medications are presented in [Listing 1](#), [Listing 2](#), and [Listing 3](#). Medications that are permitted with restrictions are listed in [Listing 4](#), [Listing 5](#), and [Listing 6](#)).

The following agents are not permitted before randomization (specific time frames are shown below) and until the last visit during the treatment period: (revised per Amendment 01)

- a) Immunoglobulin therapy and biologic drugs are not permitted within 6 months before Screening and until the last visit during the treatment period (revised per Amendment 01)
- b) Systemic immunosuppressive or immunomodulatory drugs are not permitted for a period of 5 half-lives or 60 days (whichever is longer) before randomization and until the last visit during the treatment period (revised per Amendments 01 and 03)
- c) Moderate to strong inhibitors of carboxylesterase 2 (CES2) enzyme activity are not permitted for a period of 5 half-lives or 7 days (whichever is longer) before randomization and until the last treatment visit. Simvastatin use is permitted only with QD evening administration.
- d) Live/live attenuated vaccines are not permitted within 3 months before randomization and until the last treatment visit (this does not apply to non-live/inactivated vaccines) (revised per Amendment 01)

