Concomitant therapy with AChEI or memantine should only be allowed and/or acceptable for the region or country in which the study is being conducted and should follow the local standard of care for symptomatic treatment (revised per Amendment 01). Subjects who are taking AChEI or memantine will be required to be on a stable dose for at least 12 weeks before randomization. Initiation of therapy or changing dose of AChEIs or memantine during the study should be undertaken in compliance with local standard of care for symptomatic treatment of AD. (revised per Amendment 02). Subjects who start on AChEI or memantine

or change their dose during the Treatment Period will be permitted to continue in the study; however, subjects should not undertake cognitive assessments until they have been on a stable dose for at least 4 weeks.

Subjects who are taking other medications will be required to be on a stable dose for at least 4 weeks before randomization, except for medications which are administered as short courses (eg, up to 3 weeks unless discussed and agreed with the Medical Monitor) of treatment (eg, anti-infectives, oral steroids) or which are to be used on a PRN basis. Concomitant medications (including short-term use of benzodiazepines and opiates) which are used on a PRN basis and which are central nervous system (CNS) active and may affect cognitive function are not permitted during a period of 72 hours prior to cognitive testing. (revised per Amendment 03)

For subjects who undergo an LP for collection of CSF: Subjects who are on anticoagulants may have a variable dose but should have stable anticoagulation control for at least 4 weeks before the LP procedure. Subjects may be required to stop their anticoagulant medication prior to CSF collection and then restart this medication after the LP procedure, as per local guidelines.

Either aspirin or clopidogrel (or any other antiplatelet drug which is not aspirin) is permitted in all subjects. Aspirin and clopidogrel (or any other antiplatelet drug which is not aspirin) in combination are also permitted but subjects who are on such a combination of antiplatelet drugs may be required to stop 1 or more of these antiplatelet drugs before the LP procedure and restart after the LP as per local guidelines.

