- ^d Unscheduled visits may be conducted at any time that additional assessments, including MRI scans, are clinically indicated in the judgment of the investigator. Note that not all assessments indicated under UNS Visits need be conducted – actual assessments needed will be determined by the investigator and will be based on the specific visit needs.
- ^e Only if clinically significant abnormalities are found at Visit 14 and the investigator considers it necessary to repeat at Visit 15.
- ^f Measurements of body temperature and sitting blood pressure and sitting heart rate will be obtained.
- ^g A full neurologic examination (including general status, cranial nerve function, motor system, coordination/cerebellar function, reflexes, and, sensory system) will be performed at Visit 13 (or ED). Neurologic examinations at the other visits will focus on new symptoms and signs which will then alert the investigator to consider the occurrence of new CNS pathology. Examples of neurologic symptoms and signs that may indicate new CNS pathology that may need further investigation include (but are not limited to) visual disturbance, dysarthria, dysphasia, muscle strength, limb weakness, hyperflexia, paraparesis, micturition difficulty or urgency or incontinence, ataxia, neuropsychiatric or cognitive decline in excess of expectations based on the subject's recent history.
- ^h Please refer to the Concomitant Drug/Therapy [Section 9.4.7](#), which details prohibited and permitted medications in the study and associated time frames.
- ⁱ Single 12-lead standard ECGs will be recorded. If the QTcF is greater than 450 ms, perform 2 more 12-lead standard ECGs 1 minute apart and take the mean of the 3 QTcF values.
- ^j If dipstick urinalysis performed at site is abnormal, a urine sample will be sent to the central laboratory for full urinalysis.
- ^k More frequent testing may be required per local regulations. (revised per Amendment 03) If urine dipstick pregnancy test is positive, a blood sample will be drawn for serum pregnancy testing by the central laboratory.
- ^l Viral characterization will include testing for previous exposure to CMV, HSV1, HSV2, etc.

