Immune globulin IV, IVIG, IGIV	Carimune, Flebogamma, Gamimune N, Gammagard, Gamunex, Gammar-P IV, Iveegam, Octagam, Panglobulin, Vigam, Polygam S/D, Privigen, Sandoglobulin, Venoglobulin-S
Denosumab	Prolia (revised per Amendment 01)
Other monoclonal antibodies not listed here	

^aTopical, ocular, and inhaled formulations with minimal systemic exposure need not be prohibited. (revised per Amendment 03)

Listing 3 Prohibited Live/Live Attenuated Vaccines Within 3 Months Before Randomization and Until the Last Visit During the Treatment Period (this does not apply to non-live/inactivated vaccines)

Bacterial vaccines	Viral vaccines
Bacillus Calmette-Guérin vaccine against tuberculosis	Measles vaccination
Typhoid vaccination (oral)	Mumps vaccination
Cholera vaccination (oral)	Rubella vaccination
	Oral polio vaccination (Sabin)
	Yellow fever vaccination
	Varicella (chickenpox) vaccination
	Rotavirus vaccination
	Japanese encephalitis vaccination
	Live attenuated influenza vaccine (FluMist in the United States and Canada, and Fluenz in Europe)

This list is not exhaustive

Permitted Prior/Concomitant Medications

Listing 4 Medications Which Need To Be on a Stable Dose for 12 Weeks Before the Cognitive Assessments at Visit 2 and Should Remain on the Same Stable Dose From Visit 2 to Follow Up Visit 15

Cognitive Enhancers	
Donepezil	Aricept
Rivastigmine	Exelon
Galantamine	Reminyl
Memantine	Namenda

Listing 5 Permitted Medications Used on PRN Basis Which Are Not to be Used Within 72 Hours Before Cognitive Testing

Generic name	Trade name
Opiates	
Morphine	Astramorph PF, Avinza, Depo Dur, Duramorph, Infumorph, Kadian, MS Contin, MSIR, Oramorph SR, RMS, Roxanol
Opiate Agonists	
Meperidine	Demerol, Meperitab
Fentanyl	Actiq, Duragesic, Fentora, Onsolis, Sublimaze
Codeine	Codeine
Oxycodone	Dazidox, Endocodone, Eth-OxyDose, OxyContin, OxyFast, OxyIR, Percolone, Roxicodone, Roxicodone Intensol
Other opioids or opioid agonists which are used on PRN basis	
Benzodiazepines (short-term use only, [ie, 2 to 4 weeks]) and sedatives (revised per Amendment 03)	
Estazolam	ProSom
Alprazolam	Alprazolam Intensol, Niravam, Xanax
Triazolam	Halcion
Midazolam	Versed
Lorazepam	Ativan
Flunitrazepam	Rohypnol
Temazepam	Restoril
Clonazepam	Ceberclon, Klonopin
Diazepam	Diastat, Dizac, Valium
Chlordiazepoxide	H-Tran, Librium
Flurazepam	Dalmane
Zopiclone	(various)
Zolpidem	Ambien; others
Ramelteon	Rozerem
Amitriptyline	(various)
Dothiepin	(various)
Risperidone	Risperdal
Olanzapine	Zyprexa

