Promethazine	Phenergan; others
Other benzodiazepines, tricyclic antidepressants, antipsychotics and other drugs which are used on PRN basis as sedatives	

PRN = Pro re nata

This list is not exhaustive

Listing 6 Permitted Medications

If to be used on a PRN basis see [Listing 5](#). If to be used chronically, subjects must be on a stable dose for equal or greater than 4 weeks before Randomization. Changes in dose or initiation of new concomitant medications for chronic use (not PRN use) is permitted but if the medication affects cognitive function, do not conduct cognitive testing until the dose is stable for 4 weeks.

Generic Name	Trade Name
Antidepressants	
Bupropion	Aplenzin, Budeprion, Buproban, Zyban, Wellbutrin
Nefazodone	Serzone
Rasagiline	Azilect
Selegiline	EMSAM
Isocarboxazid	Marplan
Phenelzine	Nardil
Tranlycypromine	Parnate
Citalopram	Celexa
Fluvoxamine	Luvox
Escitalopram	Lexapro
Paroxetine	Paxil, Pexeva
Fluoxetine	Prozac, Sarafem, Selfemra
Sertraline	Sertaraline, Zoloft
Duloxetine	Cymbalta
Venlafaxine hydrochloride	Effexor
Desvenlafaxine	Pristiq
Amitriptyline hydrochloride	Elavil
Clomipramine hydrochloride	Anafranil
Desipramine hydrochloride	Norpramin
Doxepin hydrochloride	Prudoxin, Silenor, Sinequan, Zonalon
Imipramine hydrochloride	Tofranil
Nortriptyline hydrochloride	Aventyl, Pamelor
Trimipramine maleate	Surmontil
Protriptyline hydrochloride	Vivactil
Amoxapine	Amoxapine
Trazodone hydrochloride	Desyrel, Oleptro
Maprotiline hydrochloride	Ludiomil
Mirtazapine	Remeron Soltab

Listing 6 Permitted Medications

Generic Name	Trade Name
Mood Stabilizers	
Carbamazepine	Carbatrol, Eptol, Equetro, Tegretol, Tegretol XR
Lamotrigine	Lamictal, Lamictal CD, Lamictal ODT, Lamictal XR
Valproic acid	Depacon, Depakene, Depakote, Depakote ER, Divalproex Sodium, Stavzor, Valproate
Antipsychotics	
Acetophenazine	Tindal
Aripiprazole	Abilify
Asenapine	Saphris
Olanzapine	Zyprexa
Chlorpromazine	Thorazine
Haloperidol	Haloperidol, Haldol
Clozapine	Clozaril, Fazaclo
Fluphenazine	Prolixin
L-Methylfolate	Deplin, L-Methylfolate Calcium
Loxapine	Loxitane
Mesoridazine	Serentil
Perphenazine	Trilafon
Quetiapine	Seroquel
Risperidone	Risperdal
Thioridazine	Mellaril
Thiothixene	Navane
Trifluoperazine	Stelazine
Benzodiazepines (short-term use only, [ie, 2 to 4 weeks]) and sedatives (revised per Amendment 04)	
Estazolam	ProSom
Alprazolam	Alprazolam Intensol, Niravam, Xanax
Triazolam	Halcion
Midazolam	Versed
Lorazepam	Ativan
Flunitrazepam	Rohypnol
Temazepam	Restoril

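### Appendix 2, Listing 4 tells sites to hold AD medication at a fixed dose to Visit 15, while Section 9.4.7 permits dose changes that two exploratory endpoints count as events

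*Protocol*

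**What the plan says.** **Appendix 2, Listing 4.** The heading covers the four cognitive enhancers. It requires 12 weeks of stable dosing before the Visit 2 cognitive assessments, then adds that the drugs "Should Remain on the Same Stable Dose From Visit 2 to Follow Up Visit 15".

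**Section 9.4.7.** "Initiation of therapy or changing dose of AChEIs or memantine during the study should be undertaken in compliance with local standard of care". Subjects who start one of these drugs "or change their dose during the Treatment Period will be permitted to continue in the study", with one condition: "subjects should not undertake cognitive assessments until they have been on a stable dose for at least 4 weeks".

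**Inclusion criterion 6 (Section 9.3.1).** Subjects on these drugs "must be on a stable dose for at least 12 weeks prior to Randomization". It sets no rule for the period after randomization.

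**Endpoints and analyses.** Section 8.3 has an exploratory objective on reducing the initiation or dose increase of other AD drugs. Section 9.7.1.1.3 turns this into two endpoints, a time to event and a proportion at 24 months. Section 9.7.1.6.3 defines the event time as running from randomization to the first dose increase or initiation. Section 9.7.1.6.1 repeats the primary analysis with efficacy data censored after a new AD drug or an increase of a current one.

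**The concern.** One protocol version gives sites two different rules for the same drugs over the same period. Under Listing 4 a subject on donepezil at Visit 2 stays on that dose until the last follow-up visit. Under Section 9.4.7 the dose may be adjusted as local care requires.

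If sites divide between the two readings, the number of dose-increase events depends partly on which page a site followed. That weakens both exploratory endpoints and makes the censored repeat of the primary analysis harder to interpret. There is also a care issue: subjects with a progressive disease could be denied a dose adjustment that the body of the protocol allows, or have a permitted change logged as a deviation.

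**Working it through.** The point turns on text, so the check is to set the passages side by side. The only arithmetic is on the schedule.

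**1. Do the two rules cover the same thing?**

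| | Listing 4 | Section 9.4.7 |
|---|---|---|
| Drugs | Donepezil, rivastigmine, galantamine, memantine | AChEIs and memantine |
| Period | Visit 2 to Visit 15 | During the study; continuation rule for the Treatment Period |
| Dose change | Dose should stay the same | Allowed under local standard of care |
| New start | Not addressed | Allowed under local standard of care |

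The conflict is on dose changes only.

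**2. Which text is out of line?** The objective, both endpoints, the event definition and the censored repeat analysis all presuppose that dose increases occur. Criterion 6 supports the first half of the Listing 4 heading and not the second. Listing 4 is therefore the outlier. Its history fits a leftover. The Section 9.4.7 sentence on initiation and dose change is marked as revised per Amendment 02, and the log for that amendment names the Synopsis and Section 9.4.7 as affected, not Appendix 2. The Listing 4 heading carries no revision mark. The preceding protocol version contains the same conflict.

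**3. Does any cross-reference settle it?** Footnote h of Table 4 sends sites to Section 9.4.7, "which details prohibited and permitted medications in the study and associated time frames". Section 9.4.7 then sends them on: "Medications that are permitted with restrictions are listed in" Listings 4 to 6 of Appendix 2. A site that follows the references meets both rules, and no order of precedence is given. Listing 6, in the same appendix, does spell out the permissive rule for other drugs: "Changes in dose or initiation of new concomitant medications for chronic use (not PRN use) is permitted". Listing 4 has no such sentence.

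**4. How far does it reach?** From Table 4, Visit 2 is week 0, Visit 13 (24 months) is week 104 and Visit 15 is week 116.
- Event window of both endpoints: weeks 0 to 104.
- Span of the Listing 4 rule: weeks 0 to 116.
- Overlap: 104/104 weeks, so no part of the event window lies outside the rule.
- Event types: dose increase and initiation. Listing 4 bears on the first, so 1 of 2.

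These figures describe reach and are not an effect size. The protocol states neither a rate of dose change nor the share of subjects on AD medication at Visit 2, so lost events cannot be estimated.

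**5. What is untouched?** The primary MMRM uses all observed post-baseline data, including data after a change in AD medication. The sample size in Section 9.7.2 (1330) uses a mean, an SD, an effect and a dropout rate, none of which depends on Listing 4.

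**The case against.** The best defence is that the two texts can be read together. The heading uses a requirement for the period before Visit 2 and only *should* for the period after, which could be a default. Section 9.4.7 then handles departures from that default, and saying that subjects may continue sounds like tolerance of an exception. A trial can ask for stable background therapy and still count or censor the changes that happen. Footnote h points to Section 9.4.7 as the operative text, no passage makes a dose change a deviation, and sites are blinded, so any damping of events would not be expected to differ by arm.

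Part of this stands. *Should* is softer than a ban, the harm depends on how sites read the appendix, and nothing shows a bias between arms. The reconciling reading, however, is not written anywhere. Section 9.4.7 also uses *should*, for following local care, and expresses no preference for keeping the dose fixed after randomization. It also refers sites to Listing 4 for the restrictions. Listing 6 shows that the authors stated permission for later changes when they meant it, although that contrast is an inference from silence.

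**Conclusion.** The concern holds and is minor. Listing 4 and Section 9.4.7 give sites incompatible instructions on changing the dose of AD medication after Visit 2, and Listing 4 is the one at odds with the rest of the protocol. The effect is confined to two exploratory endpoints (for dose increases, not initiations), the interpretation of one supplementary repeat of the primary analysis, and subjects' access to dose adjustment. The primary test and the sample size do not change.

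The practical consequence assumes that at least some sites act on the Listing 4 heading as written; how many cannot be known from the protocol. The finding applies to the protocol text carrying the Amendment 03 marks and to the version before it. The sponsor should confirm whether the heading persists in any later version.

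**What to change.** End the Listing 4 heading at the requirement of a stable dose for 12 weeks before the cognitive assessments at Visit 2. Delete the words that follow, from the *and* before "Should Remain on the Same Stable Dose From Visit 2 to Follow Up Visit 15" to the end. Add a reference to Section 9.4.7 for starts or dose changes after Visit 2. Send sites a short clarification that changes made in line with Section 9.4.7 are not protocol deviations and that the 4-week hold on cognitive assessments still applies.

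The cost is one appendix heading, one cross-reference and one site notice. Data collection, endpoints and analyses stay as they are.

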Appendix 3 Examples of AEs That May Signal Drug Abuse Potential

Categories (revised per Amendment 03)			Examples ^a	
Euphoria-related terms (revised per Amendment 03)	1	Euphoric mood	Euphoric mood	Feeling high
			Euphoria	Felt high
			Euphoric	High
			Exaggerated well-being	High feeling
			Excitement excessive	Laughter
	2	Elevated mood	Elevated mood	Elation
			Mood elevated	
	3	Feeling abnormal	Feeling abnormal	Funny episode
			Cotton wool in head	Fuzzy
			Feeling dazed	Fuzzy head
			Feeling floating	Muzzy head
			Feeling strange	Spaced out
			Feeling weightless	Unstable feeling
			Felt like a zombie	Weird feeling
			Floating feeling	Spacey
			Foggy feeling in head	
	4	Feeling drunk	Feeling drunk	Intoxicated
			Drunkenness feeling of	Stoned
			Drunk-like effect	Drugged
	5	Feeling of relaxation	Feeling of relaxation	Relaxed
			Feeling relaxed	Increased well-being
			Relaxation	Excessive happiness
	6	Dizziness	Dizziness	
	7	Thinking abnormal	Thinking abnormal	Thinking disturbance
			Abnormal thinking	Thought blocking
			Thinking irrational	Wandering thoughts
	8	Hallucination	Hallucination	Floating
Illusions			Rush	
Flashbacks			Feeling addicted	
9	Inappropriate affect	Elation inappropriate	Inappropriate elation	

Categories (revised per Amendment 03)			Examples ^a	
			Exhilaration inappropriate	Inappropriate laughter
			Feeling happy inappropriately	Inappropriate mood elevation
			Inappropriate affect	
Terms indicative of impaired attention, cognition, and mood (revised per Amendment 03)	10	Somnolence	Somnolence	
	11	Mood disorders and disturbances	Mental disturbance	Mood swings
			Depersonalisation	Emotional lability
			Psychomotor stimulation	Emotional disorder
			Mood disorders	Emotional distress
			Emotional and mood disturbances	Personality disorder
			Delirium	Impatience
			Delirious	Abnormal behavior
			Mood altered	Delusional disorder
Mood alterations Mood instability	Irritability			
Dissociative/psychotic terms (revised per Amendment 03)	12	Psychosis	Psychosis	Psychotic episode or disorder
	13	Aggression	Aggression	
	14	Confusion and disorientation	Confusion and disorientation	
	15	Dissociative State	Dissociation	Detached
			Disconnected	Sensation of distance from one's environment
			Derealisation	Loss of a sense of personal identity
			Depersonalisation	
Related terms not captured elsewhere (revised per Amendment 03)	16	Drug tolerance	Drug tolerance	
	17	Habituation	Habituation	
	18	Substance related disorders	Substance-related disorders	
Physical Dependence or Withdrawal^b (revised per Amendment 03)	18	Drug withdrawal syndrome	Drug withdrawal syndrome	Chills
			Headache	Decreased concentration
			Anxiety	Agitation
			Nausea	Irritability
			Vomiting	Sleep disturbances
			Tremor	Mood changes

- a: Examples include terminology provided in the following guidance: U.S. Department of Health and Human Services Food and Drug Administration Center for Drug Evaluation and Research. Guidance for Industry. Assessment of Abuse Potential of Drugs. January 2017. The same term may apply to more than 1 category. A more comprehensive list of terms is provided in the eCRF Completion Guidelines. (revised per Amendment 03)
- b: Only for events observed within the first 4 weeks of last dose of study drug. (revised per Amendment 03)

